5.1.3 Statistical Methods for Descriptive Secondary Objectives

Descriptive analyses on the antibody titers against meningococcal serogroups A, C, W, and Y for all subjects in each group providing a blood sample at corresponding time points (Visit 1 and Visit 4 for Group 1 and 2; Visit 5 and Visit 6 for Subgroup 1a and 2a only; Visit 7 and Visit 8 for Subgroup 1b and 2b only) using hSBA will include but not be limited to:

- hSBA meningococcal serogroups A, C, Y, and W antibody titers $\geq 1:4$ and $\geq 1:8$
- hSBA meningococcal serogroups A, C, Y, and W antibody titers ≥ 4 -fold rise
- hSBA vaccine seroresponse^a
- Titer distribution and RCDC

Descriptive analyses on the antibody responses against the antigens for the routine pediatric vaccines (Pentacel®, Prevnar 13®, M-M-R® II, VARIVAX®, RotaTeq®, and ENGERIX-B®)

- Geometric mean concentrations (GMCs)
- Proportion of subjects with vaccine response
- Proportion of subjects with concentrations meeting the specific criteria

More details related to descriptive analyses in immunogenicity responses are described in [Table 5.3](#) and [Table 5.4](#).

^a hSBA vaccine seroresponse for serogroups A, C, Y, and W is defined as:

When evaluating the immunogenicity of 3 dose series:

For a subject with a pre-1st vaccination titer $< 1:8$, the post-3rd vaccination titer must be $\geq 1:16$

For a subject with a pre-1st vaccination titer $\geq 1:8$, the post-3rd vaccination titer must be ≥ 4 -fold greater than the pre-1st vaccination titer

When evaluating the immunogenicity of 4 dose series:

For a subject with a pre-1st vaccination titer $< 1:8$, the post-4th dose vaccination titer must be $\geq 1:16$

For a subject with a pre-1st vaccination titer $\geq 1:8$, the post-4th dose vaccination titer must be ≥ 4 -fold greater than the pre-1st vaccination titer

When evaluating the effect of the 4th dose of MenACYW:

For a subject with a pre-4th dose vaccination titer $< 1:8$, the post-4th dose vaccination titer must be $\geq 1:16$

For a subject with a pre-4th dose vaccination titer $\geq 1:8$, the post-4th dose vaccination titer must be ≥ 4 -fold greater than the pre-4th dose vaccination titer

Table 5.3: Immunogenicity response to antigens in meningococcal vaccine (A, C, Y, and W-135)

Antigens, Time Points and Groups	Endpoints

hSBA meningococcal serogroups A, C, Y, and W antibody titers for Group 1 and Group 2:
 
 30 days after the 3rd dose (after the 6-month vaccination) 	
 RCDCs hSBA meningococcal serogroups A, C, Y, and W antibody titers $\geq 1:4$ and $\geq 1:8$ hSBA meningococcal serogroups A, C, Y, and W antibody titers \geq 4-fold rise from pre- vaccination (D0) to post-vaccination hSBA vaccine seroresponse

hSBA meningococcal serogroups A, C, Y, and W antibody titers:
 
 30 days after the 4th dose (after the 12-month vaccination) for Subgroup 1a and Subgroup 2a 30 days after the 4th dose (after the 15-month vaccination) for Subgroup 1b 	
 RCDCs hSBA meningococcal serogroups A, C, Y, and W antibody titers $\geq 1:4$ and $\geq 1:8$ hSBA meningococcal serogroups A, C, Y, and W antibody titers \geq 4-fold rise from pre-vaccination (D0) to post-dose 4 vaccination hSBA vaccine seroresponse

hSBA meningococcal serogroups A, C, Y, and W antibody titers to evaluate the immune persistence of MenACYW:
 
For Subgroup 1a and Subgroup 2a (persistence at 12 month), Subgroup 1a and Subgroup 1b (persistence at 12 month vs 15 month):
 
 30 days after the 3rd dose (after the 6-month vaccination) D0 before the 4th dose (before the 12-month vaccination for Subgroup 1a and before the 15-month vaccination for Subgroup 1b) 	
 hSBA meningococcal serogroups A, C, Y, and W antibody titers $\geq 1:4$ and $\geq 1:8$

Antigens, Time Points and Groups	Endpoints

hSBA meningococcal serogroups A, C, Y, and W antibody titers to evaluate the effect of 4th dose of MenACYW: For Subgroup 1a and Subgroup 1b (12 mo vs 15 mo):
 
 1. D0 before the 4th dose (before the 12-month vaccination for Subgroup 1a and before the 15-month vaccination for Subgroup 1b) 2. 30 days after the 4th dose (after the 12-month vaccination for Subgroup 1a and after the 15-month vaccination for Subgroup 1b) 	
 • hSBA meningococcal serogroups A, C, Y, and W antibody titers \geq 4-fold rise from pre-4th dose vaccination to post-4th vaccination

hSBA meningococcal serogroups A, C, Y, and W antibody titers for Subgroup 1a and Subgroup 1b (12 mo vs 15 mo):
 
 1. D0 before the 4th dose (before the 12-month vaccination for Subgroup 1a and before the 15-month vaccination for Subgroup 1b) 2. 30 days after the 4th dose (after the 12-month vaccination for Subgroup 1a and after the 15-month vaccination for Subgroup 1b) 	
 • hSBA meningococcal serogroups A, C, Y, and W antibody titers ratio (Subgroup 1b/1a) • hSBA meningococcal serogroups A, C, Y, and W antibody titers titer \geq 1:4 and \geq 1:8 • hSBA meningococcal serogroups A, C, Y, and W antibody titers \geq 1:8 difference (Subgroup 1b-1a) • hSBA meningococcal serogroups A, C, Y, and W antibody titers \geq 4-fold rise from pre-vaccination (D0) to post-4th vaccination • hSBA meningococcal serogroups A, C, Y, and W antibody titers \geq 4-fold rise from pre-4th dose vaccination to post-4th vaccination • hSBA vaccine seroresponse difference (Subgroup 1b-1a)

Table 5.4: Immunogenicity response to antigens in routine pediatric vaccines

Antigens, Time Points and Groups	Endpoints
PRP (Hib) 
 • D30 after the 6-month vaccination for Group 1 and Group 2 • D30 after the 15-month vaccination for Subgroup 1b and Subgroup 2b 	
 • GMC
To evaluate immune persistence for PRP (Hib): 
 • D30 after the 6-month vaccination for Subgroup 1b and Subgroup 2b • D0 before the 15-month vaccination for Subgroup 1b and Subgroup 2b 	
 • GMC • Proportion of subjects with concentrations $\geq 0.15 \mu\text{g/mL}$
Pertussis: PT, FHA, PRN, FIM 
 • D0 before 2-month (first) vaccination for Group 1 and Group 2 • D30 after the 6-month vaccination for Group 1 and Group 2 • D30 after the 15-month vaccination for Subgroup 1b and Subgroup 2b 	
 • GMC 
For the second time point only:
 
 • Proportion of subjects with vaccine response after the 3rd dose (using post-3rd Dose and pre-1st Dose)
To evaluate immune persistence for Pertussis: 
 • D30 after the 6-month vaccination for Subgroup 1b and Subgroup 2b • D0 before the 15-month vaccination for Subgroup 1b and Subgroup 2b 	
 • GMC
Poliovirus : type 1, type 2, type 3 
 • D30 after the 6-month vaccination for Group 1 and Group 2 • D30 after the 15-month vaccination for Subgroup 1b and Subgroup 2b 	
 • GMT
Hepatitis B 
 • D30 after the 6-month vaccination for Group 1 and Group 2 	
 • GMC • Proportion of subjects with concentrations $\geq 10 \text{ mIU/mL}$
Rotavirus: IgA 
 • D0 before first vaccination for Group 1 and Group 2 (baseline) • D30 after the 6-month vaccination for Group 1 and Group 2 	
 • GMC • Proportion of subjects with titer ≥ 4-fold rise over baseline
Tetanus, Diphtheria 
 • D30 after the 6-month vaccination for Group 1 and Group 2 And • D30 after the 15-month vaccination for Subgroup 1b and Subgroup 2b 	
 • GMC • Proportion of subjects with concentrations $\geq 0.01 \text{ IU/mL}$ • Proportion of subjects with concentrations $\geq 0.1 \text{ IU/mL}$

Antigens, Time Points and Groups	Endpoints
Pneumococcal (PCV13): • D30 after the 6-month vaccination for Group 1 and Group 2 • D30 after the 12-month vaccination for Subgroup 1a and Subgroup 2a	• GMC
Measles, Mumps, Rubella, Varicella • D30 after the 12-month vaccination for Subgroup 1a and Subgroup 2a.	• GMC

5.1.4 Statistical Methods for Observational Objectives

No hypotheses will be tested.

5.1.4.1 Statistical Methods

Safety

Safety results will be described for subjects in all study groups. The main parameters for the safety endpoints will be described by 95% Cis using the exact binomial method (Clopper-Pearson method) (15).

Safety analyses will contain at least the descriptions listed in [Table 5.5](#):

Table 5.5: Statistical analyses for safety observational objectives

Safety Events	Time and Group	Description
Immediate unsolicited non-serious systemic AE	Within 30 minutes after each vaccination in Group 1 and Group 2	Proportion of subjects that have the event, MedDRA terms, intensity, relationship to vaccine, study discontinuation, duration
Solicited injection site reactions	D0 to D7 after each vaccination in Group 1 and Group 2	Proportion of subjects that have the event, time of onset, duration, intensity, action taken, study discontinuation, number of days of occurrence, temperature collection routes
Solicited systemic reactions		
Unsolicited non-serious AE/AR	D0 to D30 after each vaccination in Group 1 and Group 2	Proportion of subjects that have the event, MedDRA terms, time of onset, duration, intensity, relationship, action taken, study discontinuation
AEs leading to study discontinuation	D0 to D30 after each vaccination in Group 1 and Group 2; D31 to next visit after each vaccination in Group1 and Group2;	Proportion of subjects that have the event, MedDRA terms, time of onset, duration, intensity, relationship,

Safety Events	Time and Group	Description
	During the whole study in Group 1 and Group 2	action taken, study discontinuation
MAAE	D0 to D30 after each vaccination in Group 1 and Group 2; D31 to next visit after each vaccination in Group1 and Group2; During the whole study in Group 1 and Group 2	Proportion of subjects that have the event, MedDRA terms, onset, duration, intensity, relationship, action taken, study discontinuation
SAE (including AESI)	D0 to D7 after each vaccination in Group1 and Group 2; D0 to D30 after each vaccination in Group1 and Group 2; D31 to next visit after each vaccination in Group1 and Group2; During the whole study in Group1 and Group 2	Proportion of subjects that have the event, MedDRA terms, onset, duration, relationship, seriousness criteria, outcome, study discontinuation

Note: “Group1 and Group2” mentioned in the above table 5.5 for safety analyses also includes the Subgroup 1a, Subgroup 1b, Subgroup 2a and Subgroup 2b, when it is applicable.

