## Synopsis

Company:	Sanofi Pasteur
Investigational Product:	MenACYW conjugate vaccine
Active Substances:	Capsular polysaccharide from meningococcal serogroups A, C, Y, and W conjugated to tetanus toxoid
Title of the Trial:	Immunogenicity and Safety Study of an Investigational Quadrivalent Meningococcal Conjugate Vaccine when Administered Concomitantly with Routine Pediatric Vaccines in Healthy Infants and Toddlers
Development Phase:	Phase III
	[REDACTED]
Trial Centers:	This will be a multi-center trial conducted at approximately 60 sites in the United States (US). Investigators and sites are listed in the “List of Investigators and Centers Involved in the Trial” document.
Planned Trial Period:	2Q 2018 to 3Q 2023
Trial Design and Methodology:	A Phase III, partially modified double-blind, randomized, parallel-group, active-controlled, multi-center study to compare the immunogenicity and describe the safety of MenACYW conjugate vaccine and MENVEO® (Meningococcal [Groups A, C, Y, and W-135] Oligosaccharide Diphtheria CRM 197 Conjugate Vaccine) when administered concomitantly with routine pediatric vaccines to healthy infants and toddlers in the US.  Approximately 2628 healthy infants aged $\geq 42$ to $\leq 89$ days will be randomized 2:1 to the following 2 groups.  Group 1 (G1): MenACYW conjugate vaccine and routine pediatric vaccines Group 2 (G2): MENVEO® and routine pediatric vaccines  Each group will be further randomized 2:1 in 2 subgroups based on the time of analyses conducted in the 2nd year of life (30 days after the 12-month vaccination or 30 days after the 15-month vaccination, respectively): Group 1: Subgroup 1a (G1a) (12 months): MenACYW conjugate vaccine and routine vaccines at 2, 4, 6, and 12 to 15 months of age Subgroup 1b (G1b) (15 months): MenACYW conjugate vaccine at 2, 4, 6, and 15 to 18 months of age and routine vaccines at 2, 4, 6, 12 to 15 months of age, and 15 to 18 months of age Group 2: Subgroup 2a (G2a) (12 months): MENVEO® at 2, 4, 6, and 12 months of age and routine vaccines at 2, 4, 6, 12, and 15 to 18 months of age

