## 5 Investigational Plan

### 5.1 Description of the Overall Study Design and Plan

#### 5.1.1 Study Design

This study is a Phase III, partially modified double-blind, randomized, parallel-group, active-controlled, multi-center study to compare the immunogenicity and safety of MenACYW conjugate vaccine and MENGEO® (Meningococcal [Groups A, C, Y, and W-135] Oligosaccharide Diphtheria CRM197 Conjugate Vaccine) when administered concomitantly with routine pediatric vaccines to healthy infants and toddlers in the US.

Approximately 2628 healthy infants aged  $\geq 42$  to  $\leq 89$  days will be randomized 2:1 to the following 2 groups:

**Group 1 (G1):** MenACYW conjugate vaccine and routine vaccines

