### 5.1.2 Justification for Study Design

The MET42 study is part of an ongoing development program that focuses on demonstrating that the safety profile of the MenACYW conjugate vaccine is similar to that of licensed MCV4, and that the immunogenicity of the MenACYW conjugate vaccine is non-inferior to licensed comparators in direct comparison trials. MET42 is a pivotal Phase III immunogenicity and safety study in which the vaccine candidate will be evaluated in infants/toddlers receiving concomitantly administered routine pediatric vaccines in the US. This study is designed to evaluate the safety and the immunogenicity of MenACYW conjugate vaccine following a 4-dose vaccination series in comparison to the licensed comparator MENVEO® in this population. Enrolment in the study will start at 6 to 8 weeks of age.

The concomitant administration of routine pediatric vaccines together with 5 different administration schedules of the MenACYW conjugate vaccine has been assessed in infants/toddlers 2 to 15 months of age in the US in study MET39. The subjects received either during or prior to the study, a number of licensed recommended vaccines at 2, 4, and 6 months of age: Pentacel®, either Prevnar® or Prevnar 13®, RotaTeq® or ROTARIX®, and ENGERIX-B® or RECOMBIVAX HB®. All subjects received M-M-R® II and VARIVAX® at 12 months. A total of 457 subjects completed the study. The immunogenicity and safety profiles of selected licensed pediatric vaccines (Pentacel®, Prevnar® or Prevnar 13®, M-M-R® II, and VARIVAX®) were assessed when administered either concomitantly with or without MenACYW conjugate vaccine. There was no evidence of interference with the pediatric routine vaccines administered concomitantly with MenACYW conjugate vaccine and the vaccine was safe and well tolerated regardless of the number of doses administered during the first year of life.

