2.3 Observational Objectives

Safety

To describe the safety profile of MenACYW conjugate vaccine and MENVEO® when administered concomitantly with routine pediatric vaccines in healthy infants and toddlers.

3 Description of the Overall Study Design and Plan

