3.1 Study Design

This study will be a Phase III, partially modified double-blind, randomized, parallel-group, active-controlled, multi-center study to compare the immunogenicity and safety of MenACYW conjugate vaccine and MENVEO® (Meningococcal [Groups A, C, Y, and W-135] Oligosaccharide Diphtheria CRM₁₉₇ Conjugate Vaccine) when administered concomitantly with routine pediatric vaccines to healthy infants and toddlers in the US.

Approximately 2628 healthy infants aged ≥ 42 to ≤ 89 days will be randomized 2:1 to the following 2 groups:

- **Group 1 (G1):** MenACYW conjugate vaccine and routine vaccines
- **Group 2 (G2):** MENVEO® and routine vaccines

Each group will be further randomized 2:1 in 2 subgroups based on the time of analyses conducted in the 2nd year of life (30 days after the 12-month vaccination or 30 days after the 15-month vaccination, respectively):

- **Group 1:**
 - **Subgroup 1a (G1a)** (12 months): MenACYW conjugate vaccine and routine vaccines at 2, 4, 6, and 12 to 15 months of age
 - **Subgroup 1b (G1b)** (15 months): MenACYW conjugate vaccine at 2, 4, 6, and 15 to 18 months of age and routine vaccines at 2, 4, 6, 12 to 15 months of age, and 15 to 18 months of age
- **Group 2:**
 - **Subgroup 2a (G2a)** (12 months): MENVEO® at 2, 4, 6, and 12 months of age and routine vaccines at 2, 4, 6, 12, and 15 to 18 months of age
 - **Subgroup 2b (G2b)** (15 months): MENVEO® at 2, 4, 6, and 12 months of age and routine vaccines at 2, 4, 6, 12, and 15 to 18 months of age

To be specific, the time of analyses as well as the collection of blood samples conducted in the 2nd year of life for Subgroup 1a and 2a is 30 days after the 12-month vaccination. The time for Subgroup 1b and 2b is 30 days after the 15-month vaccination. The schedule of vaccination and blood sampling is further detailed in [Table 3.1](#).

All subjects will receive the following routine vaccines as per the ACIP recommendations (see [Table 3.1](#)).

- Pentacel® (diphtheria, tetanus, pertussis [acellular, component]-poliovirus [inactivated]//*Haemophilus influenzae* type b [DTaP-IPV//Hib]) at 2, 4, 6, and 15 to 18^a months of age
- Prevnar 13® (pneumococcal 13-valent conjugate vaccine [PCV13]) at 2, 4, 6, and 12 to 15 months of age
- RotaTeq® (pentavalent rotavirus vaccine [RV5]) at 2, 4, and 6 months of age
- ENGERIX-B® (HB vaccine) at 2 and 6 months of age^b
- M-M-R® II (measles, mumps, rubella [MMR] vaccine) at 12 to 15 months of age

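### The documents disagree on whether the study compares safety or describes it, and the SAP pre-specifies no between-group safety estimate or interval

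*SAP*

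**What the plan says.** The design statements differ. SAP 3.1 calls the trial a "multi-center study to compare the immunogenicity and safety of MenACYW conjugate vaccine and MENVEO", and Protocol 5.1.1 has the same formulation ("multi-center study to compare the immunogenicity and safety of MenACYW"). The protocol synopsis says the study is "to compare the immunogenicity and describe the safety of MenACYW conjugate vaccine and MENVEO".

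The formal objective follows the synopsis. In both documents safety is an observational objective; SAP 2.3 words it as "To describe the safety profile of MenACYW conjugate vaccine and MENVEO". Protocol 9.1.1 and 9.2.1 state that there are no primary or secondary safety objectives, and SAP 5.1.4 states that no safety hypothesis is tested.

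On method, SAP 5.1.4.1 says "Safety results will be described for subjects in all study groups", with exact binomial 95% intervals for the main safety parameters, and Table 5.5 lists proportions and event characteristics by time window for Group 1 and Group 2. Protocol 12.1.3 plans the same. Both lists are minimum lists. SAP 5.1.5.2 describes safety subgroup analyses as being between Group 1 and Group 2, but what it lists are safety overview tables, with no difference measure.

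**The concern.** A trial described as comparing safety would be expected to say how the comparison is expressed. Here the reader gets two percentages, each with its own interval, and must judge the contrast by eye. Two single-group intervals do not directly give an interval for the difference, so they give no bound on excess risk with MenACYW. The 2:1 randomised, modified double-blind infant phase could supply that bound with no extra data.

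If between-group differences are computed later under the open-ended lists, the endpoints would be chosen after the data are known. Fixing a short list beforehand avoids that.

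**Working it through.** **Plan figures.** The documents state no safety rate, margin or precision target, so there is no safety figure to reproduce. The inputs are the planned group sizes in Protocol 6.4 (1752 and 876; 1752 + 876 = 2628) and the subgroup sizes in the synopsis (1a: 1168; 2a: 584). All event rates below are assumptions.

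**1. Expected precision, infant doses, assumed 20% in both groups.** Approximate half-width = 1.96 × √[p(1−p)(1/n1 + 1/n2)] = 1.96 × √[0.16 × (1/1752 + 1/876)] = 1.96 × √0.000274 = 3.24 points. The SAP 5.1.1.2 formula with 350/1752 and 175/876 gives −3.31 to +3.17 points.

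**2. Range over assumed rates (SAP 5.1.1.2 formula, equal rates, all randomised).**

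| Assumed rate | 95% CI of the difference (points) |
|---|---|
| 1% | −0.99 to +0.76 |
| 5% | −1.90 to +1.69 |
| 10% | −2.59 to +2.30 |
| 30% | −3.76 to +3.67 |
| 50% | −4.05 to +4.05 |

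If only 1155 and 577 contributed (the evaluable numbers for immunogenicity, a pessimistic case for a safety set), the interval would be about −1.3 to +1.0 at 1% and −4.9 to +5.1 at 50%.

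**3. What single-group intervals leave out.** Take 596/1752 (34.0%) and 263/876 (30.0%).
- Planned Clopper-Pearson intervals: 31.8 to 36.3% and 27.0 to 33.2%. They overlap.
- Wilson limits: l1 = 0.3184, u1 = 0.3627, l2 = 0.2708, u2 = 0.3314. Difference = 4.00 points.
- δ = 1.96 × √(0.3184 × 0.6816/1752 + 0.3314 × 0.6686/876) = 3.80 points.
- ε = 1.96 × √(0.2708 × 0.7292/876 + 0.3627 × 0.6373/1752) = 3.71 points.
- Interval for the difference: +0.19 to +7.70 points, which excludes zero.

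**4. Dose 4, Subgroup 1a against 2a only.** 1.96 × √[0.16 × (1/1168 + 1/584)] = 1.96 × √0.000411 = 3.97, about 4.0 points at 20%.

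**5. Where a contrast is like for like.** In Protocol Table 5.1 the two groups receive the same concomitant vaccines at 2, 4 and 6 months. At dose 4 they do not match across all subgroups. Subgroup 1b receives MenACYW at 15 to 18 months with Pentacel and HAVRIX. Both MENVEO subgroups receive theirs at 12 months with Prevnar 13, M-M-R II and VARIVAX. Subgroup 1a has the same concomitant vaccines as 2a but a wider age window (12 to 15 months). After dose 4, Subgroups 2a and 2b have a further Pentacel and HAVRIX visit; 1a has no further in-study vaccination and shorter participation (16 to 19 against 19 to 22 months).

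**The case against.** The strongest reply is that the method fits the objective. Safety is to be described, nothing is tested, and per-group percentages with exact intervals are a normal way to describe it. On that view only a word in Protocol 5.1.1 and SAP 3.1 needs changing. This largely stands, and it is why the point is an improvement and not an error.

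Three stronger readings are tempting, and the documents do not support them.
- A reader might infer that this trial sets out to show a similar safety profile. Protocol 5.1.2 presents the trial as "part of an ongoing development program that focuses on demonstrating that the safety profile of the MenACYW conjugate vaccine is similar to that of licensed" vaccines: that is the programme's focus. The trial's own objective is descriptive.
- A reader might infer that no difference can ever be estimated. The lists are open, and counts and percentages by group allow a crude difference to be worked out. What is missing is a pre-specified estimate and interval.
- A reader might infer that overlapping intervals will be taken as proof of similarity. No section states such a rule, so the 34% against 30% example shows only what the planned display leaves out.

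Descriptive status does not itself rule out a difference. Among the secondary endpoints in SAP 4.2.1.1 and in Table 5.3, the SAP already lists Subgroup 1b minus 1a differences for meningococcal responses with no hypothesis attached. The objection to a pooled dose 4 difference is sound: it would mix the vaccine effect with age and concomitant vaccines, and Protocol 6.3 accepts that second-year participants and staff may be unblinded.

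**Conclusion.** The point holds as a wording conflict and a low-cost improvement. Protocol 5.1.1 and SAP 3.1 say safety is compared; the synopsis and the objective say it is described; and only single-group intervals are pre-specified. Adding a difference for infant doses 1 to 3 would bound any excess risk to within about 3.2 points either way at a 20% event rate, and to about 0.8 to 4.1 points either way across assumed rates of 1% to 50%. These figures assume equal true rates and that all 1752 and 876 randomised children contribute. Primary conclusions and sample size are unaffected.

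**What to change.** 1. In SAP 5.1.4.1 and Table 5.5, add the Group 1 minus Group 2 difference with a 95% CI by the Wilson-score method of SAP 5.1.1.2. Label it descriptive and unadjusted, with no hypothesis test.
2. Limit it to a fixed list after each of infant doses 1, 2 and 3: any and Grade 3 solicited injection-site reaction, any and Grade 3 solicited systemic reaction, fever, and unsolicited AE, MAAE and SAE (including AESI) from D0 to D30.
3. Do not pool dose 4 across subgroups. If a dose 4 difference is shown, restrict it to Subgroup 1a against 2a within D0 to D30, and note the different age windows and possible unblinding.
4. Use the same verb, compare or describe, in the synopsis, Protocol 5.1.1 and SAP 3.1.
5. Correct the citation in SAP 5.1.4.1. It supports Clopper-Pearson with reference 15, which concerns differences between proportions; SAP section 5 cites reference 14 for the same method.

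The cost is SAP wording and one column in existing tables, using a formula the SAP already specifies. The downside is multiplicity: 8 endpoints × 3 doses = 24 intervals, of which about 24 × 0.05 = 1.2 would be expected to exclude zero by chance if there were no true differences and coverage were exactly 95%.

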#### 6.1.1.2 Preparation and Administration

MenACYW conjugate vaccine is supplied in single-dose vials (0.5 mL).

Prior to administration, all study products must be inspected visually for cracks, broken seals, correct label content (see [Section 6.2.1](#)), and extraneous particulate matter and / or discoloration, whenever solution and container permit. If any of these conditions exists, the vaccine must not be administered. A replacement dose is to be used, and the event is to be reported to the Sponsor.

The rubber stopper should not be removed from any of the vaccine vials.

After vaccine administration, the used syringe and needle will be disposed of in accordance with currently established guidelines.

Subjects must be kept under observation for 30 minutes after vaccination to ensure their safety, and any reactions during this period will be documented in the CRB. Appropriate medical equipment and emergency medications, including epinephrine (1:1000), must be available on site in the event of an anaphylactic or other immediate allergic reaction.

---

aTetanus toxoid protein quantity is approximate and dependent on the PS-to-protein ratio for the conjugates used in each formulation.

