### 12.1.3 Statistical Methods for Observational Objectives

#### *Safety / Reactogenicity*

The Safety Analysis Set (SafAS) is defined as those subjects who have received at least 1 dose of the study vaccine and have any safety data available. All subjects will have their safety analyzed for each dose according to the vaccine they actually received at that dose. Safety analysis after the full 4 doses will be conducted as well. If the vaccine received by a subject does not correspond to any study group, the subject will be excluded from the SafAS. The corresponding safety data will be presented in separate listings.

Safety analysis will include but is not limited to the following:

- The number and percentage of subjects reporting any solicited injection site reactions and solicited systemic reactions occurring from D0 to D07 after each vaccination will be summarized by study group for intensity, time of onset period, days of occurrence, and action taken.
- Immediate unsolicited systemic AEs and unsolicited AEs occurring up to D30 after each vaccination will be summarized.
- The number and percentage of subjects reporting any unsolicited non-serious AEs will be summarized by study group, intensity, time of onset period, duration, and by MedDRA preferred term and system organ class (SOC), as well as by relationship to the study vaccine.
- The number and percentage of subjects reporting at least one of any MAAEs will be summarized throughout the trial.
- The number and percentage of subjects reporting at least one of any SAEs will be summarized by study group, seriousness criterion, outcome, and by MedDRA preferred term and SOC, as well as by relationship to the study vaccine.
- The number and percentage of subjects reporting at least one of any AESIs will be summarized throughout the trial.
- Exact (Clopper-Pearson) 2-sided 95% CIs will be calculated for the percentages (57)

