4.3.2.2 Safety Endpoints

The endpoints for the evaluation of safety are:

- Occurrence, nature (Medical Dictionary for Regulatory Activities [MedDRA] preferred term), duration, intensity, relationship to vaccination, and whether the event led to early termination from the study, of any unsolicited systemic AEs reported in the 30 minutes after each vaccination
- Occurrence, time of onset, number of days of occurrence, intensity, action taken, and whether the reaction led to early termination from the study, of solicited (prelisted in the subject's diary card and electronic case report book [CRB]) injection site reactions occurring up to D07 after each vaccination
- Occurrence, time of onset, number of days of occurrence, intensity, action taken, and whether the reaction led to early termination from the study, of solicited (prelisted in the subject's diary card and book CRB) systemic reactions occurring up to D07 after each vaccination
- Occurrence, nature (MedDRA preferred term), time of onset, duration, intensity, action taken, relationship to vaccination (for systemic AEs only), and whether the event led to early termination from the study, of unsolicited AEs up to D30 after each vaccination
- Occurrence, nature (MedDRA preferred term), time of onset, duration, seriousness criteria, relationship to vaccination, outcome, and whether the event led to early termination from the

study, of SAEs (including AESIs) throughout the trial from Visit 1 to the 6-month follow-up contact after the last vaccination

- Occurrence, nature (MedDRA preferred term), time of onset, duration, intensity, action taken, relationship to vaccination (for systemic AEs only), and whether the event led to early termination from the study for MAAEs throughout the trial from Visit 1 to the 6-month follow-up contact after the last vaccination.

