4.4.2.3 SAEs (including AESIs)

An event will be considered as a serious event if “Yes” is checked for “Serious” in the CRF. An event will be considered as an AESI if “Yes” is checked for “Is the event an AESI?” in the CRF.

SAEs (including AESIs) will be analyzed throughout the study using the following periods:

- Within 7 days (D0 to D7) after vaccination
- Within 30 days (D0 to D30) after vaccination
- During the study (i.e., all SAEs occurred during the study), including the 6-month follow-up period
- During the 6-month follow-up

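### SAP Table 5.5 limits the only 30-minute summary to non-serious events, although the stated endpoint is any immediate unsolicited systemic AE

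*SAP*

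**What the plan says.** SAP 5.1.4.1, Table 5.5, has one row for the period "Within 30 minutes after each vaccination in Group 1 and Group 2", and its event type is "Immediate unsolicited non-serious systemic AE". The table is introduced as a minimum: "Safety analyses will contain at least the descriptions listed in" it.

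The endpoint list in SAP 4.3.2.2 has no such limit. It covers the occurrence and other features "of any unsolicited systemic AEs reported in the 30 minutes after each vaccination", and Protocol 9.3.2.2 has the same wording. Protocol 12.1.3 states the matching analysis: "Immediate unsolicited systemic AEs and unsolicited AEs occurring up to D30 after each vaccination will be summarized". The definitions in Protocol 9.3.2.1 and SAP 4.3.2.1 make SAEs a subset of unsolicited AEs.

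For SAEs, the shortest analysis period in SAP 4.4.2.3 is "Within 7 days (D0 to D7) after vaccination", and the SAE row of Table 5.5 also starts there. SAP 5.4.1.1, on a missing answer in the Immediate field, is again confined to non-serious systemic events. SAP 5.8, which lists changes to the planned analyses, does not mention the restriction.

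**The concern.** The event type in the analysis table is narrower than the endpoint. A statistician programming from Table 5.5 and SAP 5.4.1.1 would apply a non-serious filter to the immediate events, and the resulting proportion would not estimate the endpoint that both documents state.

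The filter removes the gravest events. Anaphylaxis that is life-threatening is serious by definition. Generalized seizures are AESIs, which SAP 4.3.2.3.4 requires to be collected as SAEs, and SAP 4.3.2.3.3 treats a febrile convulsion as an SAE. A seizure during the observation period would therefore be serious by one rule and excluded from the immediate row by another. Protocol 6.1.1.2 has the sites equipped for such cases, "in the event of an anaphylactic or other immediate allergic reaction". At stake is whether a reader of the report can see how many children had a serious reaction while still under observation.

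**Working it through.** The plan gives no figure to reproduce, so the check sets the texts side by side and follows an event through the planned outputs.

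**1. Scope of the endpoint.** SAP 4.3.2.2 and Protocol 9.3.2.2 refer to "any unsolicited systemic AEs reported in the 30 minutes after each vaccination". Since SAEs are unsolicited AEs by definition, the endpoint includes immediate SAEs.

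**2. Whether the protocol intended a limit.** In the same list in Protocol 12.1.3, the tabulation of unsolicited AEs by intensity, onset and preferred term is expressly confined to non-serious events. The statement on immediate AEs is not. The protocol uses the qualifier where it wants it.

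**3. Tracing two events, each with onset 10 minutes after injection.**

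| Planned output | Non-serious systemic AE | Serious systemic AE |
|---|---|---|
| Table 5.5, 30-minute row | counted | not counted |
| Table 5.5, D0 to D30 unsolicited row (non-serious) | counted | not counted |
| SAE row: D0 to D7, D0 to D30, whole study | not applicable | counted |
| MAAE and discontinuation rows | only if it qualifies; no period shorter than D0 to D7 | the same |

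**4. Whether the serious event can be recovered as immediate.** SAP 4.4.2.2.4 defines onset as the AE start date minus the date of the last vaccination. An event at 10 minutes gives 0 days, and so does one that evening. The two cannot be told apart by derived onset, and the shortest SAE period contains both.

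**5. Effect on the proportion.** Let n be the subjects analysed after a given vaccination, x those with at least one non-serious immediate systemic AE, and s those whose only immediate systemic AEs were serious. The endpoint is (x + s)/n. The Table 5.5 row gives x/n. The shortfall is s/n. With x = 0 and s = 1 the row shows 0 where the endpoint gives 1/n.

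**6. Whether the field exists for SAEs.** SAP 4.3.2.3.3 has SAEs entered on the AE CRF, so an Immediate response for them is likely. But SAP 4.3.2.3.1 sends SAEs in the observation period through ordinary SAE recording, and SAP 5.4.1.1 mentions the field only for non-serious events. The documents do not settle it.

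**The case against.** The strongest reply is that the split is a deliberate convention. Protocol 9.3.2.3.1 and SAP 4.3.2.3.1 give events in the 30 minutes separate routes, and SAEs join the SAE stream. The D0 to D30 unsolicited row and SAP 5.4.1.1 follow the same division. Table 5.5 is a minimum, and the contents of the sponsor's standard safety tables are not in the documents. Safety is observational with no hypotheses (SAP 5.1.4), and a zero in a row labelled non-serious is not false.

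Much of this stands. It explains how the wording arose and limits the consequence. It does not remove the mismatch: the convention contradicts the endpoint and the protocol's analysis statement, and SAP 5.8 does not declare it. A minimum list allows further outputs but specifies none for immediate SAEs.

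A reader might infer that anaphylaxis within 30 minutes would drop out of the safety analysis. The documents do not support that. The event must be reported to the sponsor within 24 hours (Protocol 10.1), and the SAE row tabulates it from D0 with its MedDRA term, onset, relationship, seriousness criteria and outcome. Nor would every immediate allergic reaction be excluded: one judged non-serious stays in the row. Protocol 6.1.1.2 names anaphylaxis to explain the emergency equipment; it gives the purpose of the observation more generally, as the subject's safety.

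**Conclusion.** The inconsistency is real and should be corrected. As specified, the immediate-AE proportion omits all serious events in the 30-minute window, and no other specified output identifies them as immediate. What is lost is their place in the immediate proportion and the immediate label, not their collection, expedited reporting or tabulation as SAEs.

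The size cannot be put as a number. The documents give no expected rate of immediate serious events, and the count of planned vaccination visits would not measure the omission. I assume such events are very rare, so that a single case could decide whether the row reads zero. I also assume the outputs follow Table 5.5 as written and that no standard table shell outside the documents already shows immediate SAEs. The correction is modest and affects no hypothesis test.

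**What to change.** Remove the non-serious qualifier from the 30-minute row of Table 5.5, so that it covers all immediate unsolicited systemic AEs, and show serious events as a sub-row. If the row is kept as it is, add at minimum a count or listing, by group and vaccination, of SAEs with onset within 30 minutes. Declaring the restriction in SAP 5.8 alone would make it open but would leave the endpoint unreported.

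Identify these SAEs from the Immediate field on the AE CRF if it is completed for SAEs. The sponsor should confirm this. Otherwise use source times or SAE narratives.

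Do not extend the rule in SAP 5.4.1.1 to SAEs. It treats a blank Immediate response as onset after the 30 minutes, so a serious reaction with a blank field would be classed as not immediate. Query a missing response for any SAE with Day 0 onset instead, before database lock.

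The cost is one wording change and one row or listing, plus a few queries or a short narrative review if the field is not available for SAEs.
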